## 9.4 Prevention of missing data

Missing data will be prevented by checking all questionnaires on completeness and correctness before the patient leaves. To correct for missing data in questionnaires, missing data will be substituted by the weighted average. When data points of IMU sensors are missing, this will be substituted by making use of interpolation. If a patient is not able to perform a certain task, this will result in a complete missing data set from the IMU sensors and TETRAS score. That specific task for this specific subject will not be used in the data analysis. When two tasks or more cannot be performed, the data from the subject will be removed from the analysis.

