## 7.3.6 Satisfaction assessment

Once the data for either the sham or intervention has been collected, the investigator removes the device from the patient's arm. The patient is then asked to fill out the satisfaction questionnaire (D-QUEST). Satisfaction is collected after both the sham and the investigational device. The investigator can help if the patient has writing difficulties. Before the patient leaves, all questionnaires will be checked thoroughly on completeness to prevent missing data.

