## 9.2 Secondary study parameter(s)

## Patient satisfaction using D-QUEST

The secondary study parameter 'patient's satisfaction' will both be assessed after the sham device and anti-tremor orthosis with the D-QUEST questionnaire. A sub-analysis per question will be performed, depicting the percentages of the total amount of patients that belong to one categorical measure (e.g., *very satisfied, not satisfied*).

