#### Potential adverse effects

All potential adverse effects – obtained from both the AEs reported from by investigator and subquestions in D-quest – will be listed with their prevalence per patient (e.g. 15% of participants displayed skin marks).

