## j. Can effects be managed?

The device can only successfully suppress tremor when the tremor is present, the damper is not utilised when there is no tremor present. When unsafe or uncomfortable situations arise, the patients may be asked to rest their arms on the table. In this position, most ET patients do not exhibit a tremor. Another way to control the effect, is to detach the orthosis directly using the designated pulling tabs which allow for quick removal.

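### Filling missing D-QUEST answers with an undefined weighted average does not fit the planned category percentages or the adverse-effect listing, and handling after early device removal is not settled

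*Protocol*

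**What the plan says.** **Missing answers.** Section 9.4 first relies on prevention: "Missing data will be prevented by checking all questionnaires on completeness and correctness before the patient leaves". For what is still missing it gives one rule: "To correct for missing data in questionnaires, missing data will be substituted by the weighted average". No weights, reference set or rounding are given, and a skipped item is not distinguished from a blank questionnaire. The same section drops a task that a patient cannot perform, and takes the patient's data out of the analysis once two or more tasks cannot be performed.

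**Planned outputs.** Section 7.1.2 describes eight device questions scored 1 to 5, plus extra questions from the manufacturer that include possible adverse effects. Section 9.2 analyses each question by "depicting the percentages of the total amount of patients that belong to one categorical measure". The adverse-effect listing in that section is "obtained from both the AEs reported from by investigator and subquestions in D-quest", with a prevalence for each effect.

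**When satisfaction is collected.** Section 3 places it after a device has been used. Section 7.3.6 gives the detailed order: "Once the data for either the sham or intervention has been collected, the investigator removes the device from the patient's arm", and the questionnaire follows.

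**Early removal.** Section 12.1, item j, foresees unsafe or uncomfortable situations and adds: "Another way to control the effect, is to detach the orthosis directly using the designated pulling tabs which allow for quick removal". Section 7.6 keeps data gathered before a withdrawal.

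**The concern.** A substitution rule has to produce values that the planned analysis can use. Here the analysis is a count of patients per answer category and a list of effects that patients report. An average is neither of these. The rule also ignores the reason for the gap. If an answer is missing because the device was uncomfortable, a value borrowed from patients who kept it on points the wrong way.

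Usability and comfort is the first secondary objective (Section 2.2), and Section 6.4 says the feedback will guide the design of the orthosis. What is at stake is whether the satisfaction table shows what patients answered, and whether those who could not tolerate a device remain visible in it. The primary endpoints are not affected.

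**Working it through.** The protocol gives no figure for missing D-QUEST data or for early stopping, so there is nothing to reproduce. The check sets the rules against the outputs and then illustrates the size.

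**1. One skipped item.** Inputs: eight device questions, whole scores from 1 to 5 (Section 7.1.2). Two readings of the average are possible; the answers below are assumed.
- *The patient's own other items.* Seven answers of 4, 4, 4, 3, 5, 4, 3 sum to 27, and 27/7 = 3.86.
- *Other patients' answers to the same item.* If 24 answers sum to 92, 92/24 = 3.83.

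Neither value is a category. With equal weights the result is whole only if the sum divides exactly by 7 or by 24, and unequal weights do not cure this. Rounding would force a category, but none is stated, and the table would then contain an answer that nobody gave. No early stopper is needed for this problem to arise.

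**2. One missing adverse-effect sub-question.** The answer format is not given; assume yes = 1 and no = 0. If 3 of 24 other patients report an effect, the filled value is 3/24 = 0.125. That is neither a reported effect nor its absence, so it cannot enter a listing or a numerator.

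**3. Device removed early, questionnaire not completed.** There are seven tasks per condition. A patient who stops during task *j* lacks 8 − *j* tasks: one if *j* = 7, two or more if *j* ≤ 6.

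| Reading | Result for D-QUEST |
|---|---|
| Section 3: satisfaction is assessed after use of a device | Questionnaire given; nothing is missing |
| Section 9.4 average, taken from other patients | Patient receives others' satisfaction |
| Section 9.4 average, taken from the patient's own items | Nothing to average if the form is blank |
| Section 9.4 two-task rule, if it covers stopping and D-QUEST (*j* ≤ 6) | Patient leaves the table |
| Section 7.6, if the patient withdraws | Data already gathered are used; nothing is said about the blank form |

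The text does not choose between these readings.

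**4. Size, on assumed figures.** Take 25 patients who wear the device and *k* who stop and leave no questionnaire. Completers average 3.5 to 4.0 on an item, stoppers would have scored 1 to 2, and scores of 1 and 2 count as dissatisfied.
- Overstatement of the item mean = *k* × (completers' mean − stoppers' score)/25. The smallest gap is 3.5 − 2 = 1.5 and the largest is 4.0 − 1 = 3.0.
- Dissatisfied share hidden by substitution = *k*/25.

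| *k* | Mean overstated by | Share hidden |
|---|---|---|
| 1 | 0.06 to 0.12 | 4% |
| 2 | 0.12 to 0.24 | 8% |
| 3 | 0.18 to 0.36 | 12% |
| 4 | 0.24 to 0.48 | 16% |

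Under removal the reported mean is also the completers' mean, so the overstatement is the same. The hidden share is slightly smaller if some completers are dissatisfied. With *k* = 3 and two dissatisfied completers, the true share is 5/25 = 20.0%. Removal gives 2/22 = 9.1%, and substitution gives 2/25 = 8.0%. Section 9.2 plans percentages and no mean, so the right-hand column is the relevant one.

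**The case against.** A reader might infer more: that D-QUEST is given only after a complete recording, so that anyone who stops early is counted as averagely satisfied. The protocol does not support that chain.
- Section 7.3.6 describes the usual order and does not bar the questionnaire after early removal. Section 3 makes use of the device the trigger. The patient is still in the room, and forms are checked before departure.
- A patient who stops before the last task may be removed under the two-task rule and not averaged at all.
- Nothing says that the average comes from patients who tolerated the device. It may be meant for isolated gaps, filled from the patient's own answers.
- Self-reported adverse effects are not simply lost. Section 7.3.7 has every observed event reported throughout the visit, Section 8.2.1 records spontaneous reports, and the form in Appendix II has a code for a stopped intervention.

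The size is also open to challenge. Every score above is assumed. The 10% drop-out figure in Section 4.4 is a general allowance and not a rate of stopping for discomfort. Section 7.5 does not expect many drop-outs. Recording takes 7 × 30 s = 3.5 minutes per condition, and wear is short (30 minutes per device in Section 12.2, an hour in Section 10.4). The endpoint is secondary, with no test planned.

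These objections stand, and they limit the point. They do not answer steps 1 and 2, which hold under either reading of the average. Nor do they settle step 3, where the protocol leaves the choice open.

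**Conclusion.** The point holds in limited form. The substitution rule is stated without condition and does not fit either planned use of D-QUEST. This rests on the text alone and does not depend on why answers are missing.

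The second part is conditional. If a device comes off early for discomfort and the questionnaire is not completed, both substitution from other patients and removal would make satisfaction look better than it was, and the protocol does not say which applies. The size is unknown and probably small: up to 4 percentage points per such patient among 25, assuming that the patient would have answered in a dissatisfied category. Some detail from the D-QUEST sub-questions could be lost, but observed and spontaneously reported events are still recorded. The primary analyses and the sample size are unaffected.

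**What to change.** - **Section 9.4:** delete the weighted-average substitution for D-QUEST and its sub-questions. State that the two-task removal rule applies to TETRAS and IMU data only.
- **Section 9.2:** report observed answers per category for each device, with all patients who wore that device as the denominator. Add a row for *not answered*, so that the categories and this row sum to 100%. Show *device stopped early* as a separate row. A patient who stopped early and did answer appears there and also in the answer category. List sub-question effects as reported, with the number unanswered.
- **Section 7.3.6:** align with Section 3 by stating that D-QUEST and its sub-questions are given after any use of a device, including early removal.

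The cost is a short wording change. No visit is added, because the patient is still present, and no rule on when a device is removed is touched. The one downside is that a few items will be shown as missing and not filled in.

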## 5. TREATMENT OF SUBJECTS

## 5.1 Investigational product/treatment

The device that will be tested in this study is the STIL anti-tremor orthosis. This non-invasive passive device uses the principle of applying external joint damping as its working principle. Two types of dampers are used to restrict high frequency involuntary motion, leaving low impact on voluntary motion, to passively suppress the forearm tremor. This will support ET patients in their daily and social activities.

A sham device is used to investigate and eliminate the influence of the weight of the STIL orthosis on tremor suppression and to validate the working principle of the dampers. The sham device used has no damping elements, but has a similar look and weight (see *IMDD chapter 1.1.i*).

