## 7.6 Follow-up of subjects withdrawn from treatment

Subjects that withdraw from the study, will not be followed or contacted for future research. Data that was already collected until the moment of withdrawal, will be used for the study.

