## Tremor amplitude using IMU data

Tremor amplitude is measured during the performed tasks by taking the data from the IMU that is attached to the fingers. Likewise, this endpoint score will be compared over the two conditions using two-tailed matched pairs t-test, to analyze the difference in tremor amplitude. Again, the data will be checked for normal distribution, and the effect of the sham device will be evaluated.

The mean reduction in tremor severity according to both TETRAS rating and tremor amplitude of the hand are the co-primary endpoints. Sub analyses will be performed to evaluate the effect of the orthosis on these endpoints during the different tasks. This will be done to analyze the effect of the orthosis on specific tremor types: kinetic tremor (eating, drinking, pouring and spiral drawing), postural tremor (forward outstretched posture, lateral wing beating posture) and intention tremor (finger-to-nose).

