## e. Analysis of potential effect

The orthosis is equipped with passive dampers which exert an additional damping to the respective joint. In this manner, high frequency involuntary movement, such as tremor, is suppressed but voluntary motion is still allowed. This will have a positive effect on the functional and social life of the patient.

The orthosis is made as save as possible, by implementing precautionary measures in order to minimize the risks for the patient. The following list consists of possible situations with a high-risk index value, which are generally unacceptable, that could occur during the clinical trial. After performing the precautionary measures, the residual risk index value could be considered acceptable. A more detailed list of precautionary measures to avoid hazardous situations is conducted in Appendix VI of the IMDD.

I. The user appears to be allergic to a certain substance present in the device, triggering an allergic reaction, which could possibly result in redness of the skin of even the need for medication.

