#### APPENDIX I - INSTRUCTIONS ON HOW TO EVALUATE TREMOR PER DOF

TETRAS makes use of different rating scales to rate tremor in different tasks. *Figure 8* displays the three different scales used to assess the tasks relevant to STIL. Tasks consist of the forward outstretched posture, lateral "wing beating" posture, finger-to-nose manoeuvre, spiral drawing, pouring, drinking and eating.

Every posture and ADL task will be scored using the *upper limb tremor scale*. Also, all the different DOFs will be assessed using this scale. Instructions can be found on the next pages, distance between movements is absolute. The ADL tasks will also be scored using the *ADL task scale*, to assess the performance of the exercise.

To assess the spiral drawing, the *spiral scale* will be used. In the video footage two spirals are shown, only assess the first bigger spiral. The scores are defined by whole numbers. However, 0.5-point increments may be used it a rating cannot be reconciled to the higher or lower whole number. Use *figure 9* to fill out your scores.

	RATING SCALE		
Score	Upper limb tremor	Spiral	ADL tasks
0	None	Normal	Normal
0.5	-		
1	< 0.5 cm	Slight; barely visible	Slighty abnormal; presen but does not
			interfere
1.5	0.5 - < 1 cm		
2	1 - < 3 cm	Mild; obvious tremor	Mildy abnormal; some difficulty but can
			complete tasks (little spill)
2.5	3 - < 5 cm		
3	5 - < 10 cm	Moderate; parts not	Moderately abnormal; big spill, change of
		recognizable	strategy
3.5	10 - < 20 cm		
4	≥ 20 cm	Severe; figure not recognizable	Severely abnormal. Cannot do it

Figure 8: TETRAS scales

Patient										
Scale	Upper I	imb trem	nor			Spiral ADL tasks				
Item	Streched	Wing	Nose	Pouring	Drinking	Eating	Spiral	Pouring	Drinking	Eating
Overall										
SIER								$\triangleright$	>	$>\!$
EFE								$\triangleright$	$>\!$	$>\!$
FPS								$\triangleright$	>	$>\!$
WFE								$\triangleright$	$>\!$	$>\!$
FFE								$\geq$	$\geq$	$\geq$

Figure 9: Scoreform

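### Section 9.4 deletes tasks a patient cannot perform, and the patient at two or more, although Appendix I scores inability at eating, drinking and pouring as 4

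*Protocol*

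**What the plan says.** Section 9.4 of the protocol lets inability to perform a task make both the TETRAS score and the IMU data for that task missing. For one such task it says: "That specific task for this specific subject will not be used in the data analysis". For more than one it says: "When two tasks or more cannot be performed, the data from the subject will be removed from the analysis". Neither sentence names a condition or a cause of the inability.

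Appendix I describes the same event as an outcome. Pouring, drinking and eating are rated twice: on the upper limb scale for tremor amplitude, and on the ADL task scale "to assess the performance of the exercise". The top category of the ADL task scale, score 4, reads "Severely abnormal. Cannot do it".

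The TETRAS co-primary is the sum of seven tasks, with a maximum of 28 points per condition (7.1.1). It is compared in pairs, baseline against orthosis and sham against orthosis (7.3.5, 9.1).

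**The concern.** In a within-patient comparison of devices, failing a task while wearing one of them is a result obtained under that condition. The scale has a value for that result on three items, and 9.4 discards the value. Who stays in the analysis then depends partly on how patients fared under the conditions being compared.

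The mechanism is plausible in both directions. Section 6.2 reports that, in healthy subjects, stronger damping hindered voluntary movement too much, so the orthosis could make a task harder for some patients. The inclusion criteria also select patients with marked disability, so some may fail a task at baseline and manage it with the orthosis. The first case should count against the device and the second for it; 9.4 removes both. Because the rule works by patient and not by comparison, two tasks failed only with the sham would also take the patient out of the baseline comparison.

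At stake is the size of the mean TETRAS change that is reported, and whether a reader can tell which way the deletions moved it.

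**Working it through.** **The plan's own figure.** Section 4.4 and Figure 3 use means of 14 and 10, SD 5 in each condition and correlation 0.5.
- SD of the difference = sqrt(25 + 25 - 2 × 0.5 × 25) = 5, so dz = 4/5 = 0.8.
- With two-sided alpha 0.0125 and n = 21, the noncentrality is 0.8 × sqrt(21) = 3.666, the critical t is 2.744 and power is 0.810.
- The stated 21 patients is reproduced, and the sample size is not in dispute.

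**Which scale feeds the total.** Section 4.4 counts three tasks with half points and four without: 3 × 9 + 4 × 5 = 47 steps. That fits the two postures and finger-to-nose on the upper limb scale (nine levels), and the spiral, eating, drinking and pouring on whole-point scales (five levels). On this reading, items with an explicit score for inability carry 3 × 4 = 12 of 28 points (43%).

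**Illustration: two ADL tasks impossible with the orthosis.**
- From 4.4: a mean change of -4 points. Assumed: spread evenly over seven tasks, -4/7 = -0.571 each.
- Assumed: comparator item score b of 2 to 3. The example baseline of 14 is 2 per task.
- Change for such a patient, scored = 5 × (-0.571) + 2 × (4 - b), which is +1.14 at b = 2 and -0.86 at b = 3.
- Mean over 25 patients with k affected = [(25 - k) × (-4) + k × change]/25.

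| k | b = 2 | b = 3 | After removal under 9.4 |
|---|---|---|---|
| 1 | -3.79 | -3.87 | -4.00 |
| 2 | -3.59 | -3.75 | -4.00 |
| 4 | -3.18 | -3.50 | -4.00 |

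The benefit is overstated by 0.13 (k = 1, b = 3) to 0.82 points (k = 4, b = 2).

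**One task impossible with the orthosis.** Dropping it from both conditions leaves 6 × (-0.571) = -3.43. Scoring it gives -3.43 + (4 - b), that is -1.43 (b = 2) or -2.43 (b = 3). That patient's change is flattered by 1 to 2 points.

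**Reverse case: two tasks impossible at baseline, orthosis item score b.** Change = 5 × (-0.571) + 2 × (b - 4), which is -6.86 (b = 2) or -4.86 (b = 3). With k = 1 to 4, removal understates the mean benefit by 0.03 to 0.46 points.

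**Loss of patients.** Removing 4 of 25 leaves 21 and power 0.81. Removing 5 leaves 20 and power 0.783.

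**The case against.** **Reach of the anchor.** Only the ADL task scale scores inability, so three of seven tasks are affected. The postures and finger-to-nose are rated in centimetres, and a spiral score of 4 means an unrecognisable figure. Section 4.2 rates the ADL tasks on the upper limb scale for inclusion, and the protocol never says outright that the ADL scale enters the 28-point total. This stands as a limit: the link to the co-primary is inferred from the count in 4.4.

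**A failed attempt may still be rated.** Sensors and video run while a task is attempted, so a failed attempt could leave a recording and receive a 4, and 9.4 might be meant only for tasks never attempted. That would reconcile the two sections, but the text does not draw the line: in 9.4, inability itself makes the TETRAS score missing.

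**Direction and size.** A reader might infer that 9.4 favours the device. The documents do not support that, because the rule deletes baseline inability as well and no frequency is given. The upper end of the illustration needs four of 25 patients to fail two of the three tasks because of the orthosis, and the dampers were chosen to limit obstruction (6.2, 12.1a).

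**Voluntary motion.** Section 5.1 says of the device: "Two types of dampers are used to restrict high frequency involuntary motion, leaving low impact on voluntary motion". A reader might infer that the IMU analyses are deficient because all of them concern tremor amplitude. They match the stated objectives, however, and sparing of voluntary motion is neither an objective nor an endpoint. Usability is asked about through D-QUEST and added questions (7.1.2). A further IMU analysis would be a new exploratory endpoint, not a correction.

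**Contrast with withdrawal.** Section 7.6 says: "Data that was already collected until the moment of withdrawal, will be used for the study". A reader might see an inconsistency with 9.4. It is weak, because both primary comparisons need orthosis data, so baseline and sham data alone could enter neither. What 9.4 really loses in addition is the tasks that a removed patient did perform, up to five of seven.

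**Conclusion.** The point holds as a minor one. For eating, drinking and pouring, 9.4 discards a value that Appendix I assigns, and removing the patient at two or more tasks makes inclusion in the TETRAS comparison depend on outcome. The net direction is unknown.

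The figures (a reported -4.0 against -3.9 to -3.2 when the orthosis causes the inability, and a benefit understated by 0.03 to 0.46 points in the reverse case) show what the rule can do. They are not estimates. They rest on the example in 4.4, an even spread over tasks, item scores of 2 to 3, 1 to 4 affected patients of 25, and the inference that the ADL scale feeds the total. If the upper limb scale were used for these three items, the protocol would have no score for inability in the co-primary, and the contradiction would be confined to the separate ADL ratings.

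An IMU amplitude cannot be obtained for a task not performed, so the Appendix I score does not resolve the IMU co-primary.

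**What to change.** - In 9.4, score 4 on the eating, drinking or pouring item in any condition in which the patient cannot do the task. Keep these patients in the TETRAS co-primary, using the tasks they did perform, at least as a prespecified sensitivity analysis. State that these three items enter the total on the ADL task scale, if that is the intention.
- For the IMU co-primary, drop only the unperformed task and keep the patient's other tasks.
- Report unperformed tasks and removed patients by condition (baseline, sham, orthosis) and reason, and read the IMU result alongside that listing.

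The cost is a short text change and a little more analysis of data already being collected, with no extra patients or visits and no effect on the Bonferroni alpha. The TETRAS result may become less favourable to the device, and the score of 4 covers only three of the seven tasks.
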